1 STUDY SYNOPSIS

Study Title	A Multicenter, Randomized, Double-Blind, Placebo-Controlled, Multiple Dose Study to Evaluate Safety, Tolerability and Efficacy of Orally Administered ENT-01 for the Treatment of Parkinson's Disease-Related Constipation (KARMET)
Protocol Number	ENT-01-030
Study Phase	2b
Methodology	
This first part of this study was conducted as a multicenter, randomized, double-blind, placebo-controlled study. A subject's total study duration was no more than 10 weeks and total active dosing days was a maximum of 25 days. Approximately 72 subjects were randomized 3:1 to treatment or placebo (double-blind), with approximately 54 subjects allocated to the treatment groups and approximately 18 to placebo.
 
In this amendment, up to an additional 80 subjects (approximately) will be randomized 1:1 to treatment or placebo (double-blind) with approximately 40 subjects allocated to each group.
 
Randomization will be stratified on baseline weekly CSBM rate. Subjects with a baseline weekly CSBM rate of 1-3.0 will start with 3 tablets daily (3 placebo tablets or equivalent to 75 mg of ENT-01 if randomized to active treatment), while subjects with a baseline weekly CSBM rate of 0 - 0.9 will start with 6 tablets daily (6 placebo tablets, or equivalent to 150 mg of ENT-01 if randomized to active treatment).
 
Dose will then be increased by 25 mg (or 1 placebo tablet) every three days, until an effective dose is reached, up to a maximum dose of 10 tablets (i.e., 250 mg of ENT-01 if randomized to active treatment) or maximum tolerated dose (MTD) is reached, whichever comes first.
 
After completing up to 25 days of dosing, all subjects will be given placebo for 2 weeks (single-blind) followed by 4 weeks of wash-out.
 
The study will be conducted on an out-patient basis. Each subject will have 6 visits to the clinic: Visit 1/Screening Visit; Visit 2/Randomization Visit; Visit 3/Follow up Visit (during the dosing period); Visit 4/Single-Blind Placebo Withdrawal Period Visit; Visit 5/Washout Period; and Visit 6/ End of Study Visit.

Study Duration	Each subject will participate in the study for approximately 10 weeks. The duration of the amended study, from first subject enrolled to last subject last visit, is anticipated to be 6 to 9 months.
Study Centers	This is a multicenter trial at up to 25 U.S. sites.

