4.2 Visit 2: Randomization (Study Day 1 + 8 days)

The purpose of this period is to establish the prokinetic dose for subjects randomized to treatment (or placebo). The prokinetic dose is the dose that results in a CSBM on all three dosing days at any given dose. Subjects will also be required to have a CSBM on at least 1 of 2 subsequent days at the “fixed” dose. In other words, *the dose will only be “fixed” for the remainder of the treatment period if the subject has CSBMs on at least 4 of 5 consecutive days at a given dose.*

In this amended study, subjects will be randomized in a 1:1 ratio to receive either ENT-01 or placebo depending on baseline weekly CSBM rate:

- Subjects with baseline CSBMs of 0-0.9 will be randomized to begin treatment with 150 mg of ENT-01 or 6 tablets of placebo.
- Subjects with baseline CSBMs of 1.0-3.0 will be randomized to begin with 75 mg of ENT-01 or 3 tablets of placebo.

Subjects will self-administer the study medication at home, beginning the day after Visit 2. The dose will be taken upon awakening on an empty stomach along with 8 oz. of water. The subject will be instructed to remain in the upright position for the next 60 minutes. This can be in the sitting or standing position, and the subject should be encouraged to walk around, go to the kitchen and make a cup of tea or coffee (with or without milk or sugar), to watch the news or read a paper in the upright position. The subject will also be instructed to not eat for at least 60 minutes thereafter.

After the first dose, the subject will be advised to stay home for 4-6 hours in case an emergency evacuation occurs. The subject can determine what to do after subsequent doses. Subjects are not allowed to miss a dose, however, in the event this does happen, subjects must wait a minimum of 5 hours post ingestion of a meal and at least 1 hour prior to the next meal to take the missed dose.

Any given dose is repeated for 3 consecutive days. If the subject has not produced a CSBM

within 24 hours of a dose on all three days at the initial dose, then they will increase their daily dose by 1 tablet (i.e., 25 mg for active treatment), repeating that dose for three consecutive days. This 3-day incremental dosing will continue until the subject:

- Reaches the prokinetic dose. The prokinetic dose is determined when a subject has entered CSBMs on at least 4 of 5 consecutive days at a given dose. The subject then remains on that dose until Visit 4;

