2. STUDY DESIGN

2.1. Synopsis of Study Design

This study will be conducted as a multicenter, randomized, double-blind, placebo-controlled study in patients with Parkinson's Disease and constipation.

This study has two parts. The first part of this randomized approximately 72 subjects in a 3:1 to treatment or placebo ratio (double-blind), with approximately 54 subjects allocated to the treatment groups and approximately 18 to placebo. In the second part of the study, an additional 80 patients (approximately) will be randomized 1:1 to treatment or placebo (double-blind) with approximately 40 subjects allocated to each group.

In both parts of the study, the study was conducted as a multicenter, randomized, double-blind, placebo-controlled study. A subject's total study duration was no more than 10 weeks and total active dosing days was a maximum of 25 days.

During the active dosing period, patients will be able to increase/adjust their dose every three days. This is called the Dose Adjustment period. After the subject documents two complete spontaneous bowel movements in three days, the subject will fix at the dose for the remainder of the study. This is called the Fixed Dose period. After completing up to 25 days of dosing, all subjects will be given placebo for 2 weeks (single-blind) followed by 4 weeks of wash-out.

Figure 1. Visit Schedule Overview					
Visit 1	Visit 2	Visit 3	Visit 4	Visit 5	Visit 6
Screening	Randomization and Drug Dispensation	Follow up	Single Blind Placebo Withdrawal	Wash Out	End of Study
Day -14	Day 1	Day 11 +/- 1 day	Day 25 - 3 days	Day 39 +/- 2 days	Day 69 +/- 3 days

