2.5. Study Periods

The study consists of the following periods:

1. **Screening Period:** This period lasts from Visit 1 to the day before Visit 2 (Day of randomization)
2. **Treatment Period:** This period lasts from Visit 2 (day of randomization) to the day before Visit 4 (start of single blind placebo period) and is divided into two sub-periods
 - 2.1. **Dose Escalation Period:** This period starts at Visit 2 and ends when the subject is on a Fixed Dose of study medication.
 - 2.2. **Fixed Dose Period:** This period starts when the subject is on a Fixed Dose of study medication and lasts until Visit 4. The fixed dose period is only defined if the subject was in the treatment period for at least seven days after the date of randomization. In the event that a subject is on the same dose until the start of the single blind placebo period or until withdrawal from treatment after being in the treatment period for at least seven days after randomization, then the fixed dose period will be the entire treatment period and the dose escalation period will not be defined. If the subject was not on their fixed dose for at least seven days, then the fixed dose period will extend to the subject's last seven days of treatment (including fixed dose) in order to derived rate variables during the fixed dose period, as described in Section 4.7. Missing diary entries in the middle of treatments of the same dose are not considered when determining the start of the fixed dose period.
3. **Single Blind Placebo Withdrawal Period:** This period starts at Visit 4 and ends at Visit 5. Weekly rate derivations during the single blind placebo withdrawal period will not include assessments on the Visit 4 date.
4. **Wash Out Period:** This period starts at Visit 5 and ends at Visit 6.

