4.8. Safety Analyses

All safety analyses will be conducted on the Safety Population. The safety data will be presented in individual listings and summary tables. Descriptive statistics will be used to summarize the safety data by period and both by treatment group and overall. The denominator for calculating the percentages will be based on the number of subjects on each treatment arm (ENT-01 or placebo) and overall in the Safety Population. The summary for the ENT-01 arm during the Fixed Dose period will also be broken down to the fixed dose levels.

No formal hypothesis-testing analysis of safety data will be performed.

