4.8.8 Columbia-Suicide Severity Rating Scale (C-SSRS)

The number and percentage of patients with Suicidal Ideation, Suicidal Behavior, and Self-Injurious Behavior without Suicidal Intent based on the Columbia-Suicide Severity Rating Scale (C-SSRS) during the treatment period will be summarized by treatment group. Treatment-emergent Suicidal Ideation, Suicidal Behavior, and Self-Injurious Behavior without Suicidal Intent will be based on Visit 3 through End of Study (EOS)/Early Termination (ET). In this summary, the number and percentage of patients who experience the particular event at least once during the treatment period will be summarized. The particular events are:

- Suicidal Ideation (1-5)
 1. Wish to be Dead
 2. Non-specific active suicidal thoughts
 3. Active suicidal ideation with any methods (not plan) without intent to act
 4. Active suicidal ideation with some intent to act, without specific plan
 5. Active suicidal ideation with specific plan and intent
- Suicidal Behavior (6-10)
 6. Preparatory acts or behavior
 7. Aborted attempt
 8. Interrupted attempt
 9. Non-fatal suicide attempt
 10. Completed suicide
- Self-injurious behavior without suicidal intent

For the composite endpoint of suicidal ideation (Categories 1-5), the number and percentage of patients who experience any one of the five suicidal events at least once during the treatment period will be summarized by treatment group. For the composite endpoint of suicidal behavior (Categories 6-10), the number and percentage of patients who experience any one of the five

suicidal behavior events at least once during the treatment period will be summarized by treatment group.

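### The C-SSRS treatment-emergent summary runs from Visit 3 to end of study but is labelled as the treatment period, which SAP 2.5 ends the day before Visit 4

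*SAP*

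**What the plan says.** SAP 4.8.8 opens by summarizing suicidal ideation, suicidal behavior and non-suicidal self-injury over the treatment period, by arm. It then says that treatment-emergent events "will be based on Visit 3 through End of Study (EOS)/Early Termination (ET". The next sentence, still about the same summary, counts patients who "experience the particular event at least once during the treatment period will be summarized". The composite tables and the two shift tables repeat the treatment-period label and give no visit range.

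SAP 2.5 defines the Treatment Period: "This period lasts from Visit 2 (day of randomization) to the day before Visit 4". SAP 4.8.2 uses the same name for dose escalation and fixed dose combined, and lists single-blind placebo, washout and entire study as separate adverse event summaries.

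The general rule in SAP 4.8 is: "Descriptive statistics will be used to summarize the safety data by period and both by treatment group and overall". SAP 4.8.8 names no periods of its own.

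After the double-blind phase, the Protocol synopsis says, "all subjects will be given placebo for 2 weeks (single-blind) followed by 4 weeks of wash-out". Protocol 9.2.2 specifies the since-last-visit form of the C-SSRS at every time point after screening.

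**The concern.** One clinical study report would use one label for two windows. Suicidal ideation arising on Day 50 would be a washout event in the adverse event tables and a treatment-period event in the C-SSRS table. Without going to the listings, a reader could not tell whether an event in the ENT-01 column arose on drug or weeks after the last dose.

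On-drug events and post-withdrawal events answer different safety questions, and a single pooled count answers neither cleanly. The programmer also has no settled instruction for the composite and shift tables, because the label they carry has two meanings in the same SAP.

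**Working it through.** **Inputs.** Active dosing: "total active dosing days was a maximum of 25 days" (SAP 2.1), with the first dose at home "beginning the day after Visit 2" (Protocol 4.2). Then 2 weeks of placebo and 4 weeks of washout. Nominal visit days in Protocol Table 1: Visit 2 on Day 1, Visit 3 on Day 11, Visit 4 on Day 26 (minus 2), Visit 5 on Day 39, Visit 6 on Day 69 (plus or minus 8).

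**The plan's own duration.** 25 + 14 + 28 = 67 days = 9.6 weeks, which agrees with the stated maximum of 10 weeks (screening not counted).

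**Share of time off ENT-01.**
- From the stated phases: (14 + 28)/67 = 42/67 = 63%.
- From nominal visit days: (69 − 26)/(69 − 1) = 43/68 = 63%.
- With the Protocol windows for Visits 4 and 6: lowest (61 − 26)/(61 − 1) = 35/60 = 58%; highest (77 − 24)/(77 − 1) = 53/76 = 70%.
- Counting literally from the Visit 3 date: 43/(69 − 11) = 43/58 = 74%. The 68-day base is the fairer one, because the Visit 3 form looks back to Visit 2.

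**By assessment.** Visit 3 covers Visit 2 to Visit 3, and Visit 4 covers Visit 3 to Visit 4; both intervals lie in the dosing phase. Visit 5 covers the placebo phase and Visit 6 the washout. So two of four scheduled assessments cover only off-drug time.

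**Effect on the counts (illustration).** The documents give no event rates. Assume a constant background hazard *h* per week in both arms, a hazard *k* times as high on ENT-01 while dosed, and no effect after the last dose. With 25/7 = 3.57 weeks on drug and 43/7 = 6.14 weeks off:
- On-drug table: P = 1 − exp(−*kh* × 3.57) for ENT-01 and 1 − exp(−*h* × 3.57) for placebo.
- Pooled table: P = 1 − exp(−*h*(3.57*k* + 6.14)) for ENT-01 and 1 − exp(−*h* × 9.71) for placebo.

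For *h* = 0.5% per week and *k* = 3:
- On drug: 5.22% against 1.77%, ratio 2.95, difference 3.45 points.
- Pooled: 8.08% against 4.74%, ratio 1.70, difference 3.34 points.

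For *h* from 0.1% to 1% per week:

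| *k* | Ratio, on drug | Ratio, pooled | Difference in points, on drug → pooled |
|---|---|---|---|
| 2 | 1.96–2.00 | 1.34–1.37 | 0.36 → 0.35 to 3.39 → 3.18 |
| 3 | 2.90–2.99 | 1.68–1.73 | 0.71 → 0.70 to 6.65 → 6.26 |
| 5 | 4.66–4.96 | 2.30–2.45 | 1.41 → 1.40 to 12.85 → 12.08 |

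The ratio shrinks and the difference barely moves. With about 54 + 40 = 94 subjects on ENT-01, the *h* = 0.5%, *k* = 3 case gives 4.9 expected subjects with an event on drug and 7.6 in the pooled table. About 2.7 would be counted under a treatment-period label only because of an event after drug had stopped.

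**The case against.** Much of the case on the other side stands.

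- **Handled elsewhere.** SAP 4.8 already says that safety data are summarized by period, and SAP 4.8.8 provides patient listings. This helps, but a general sentence does not override the specific visit range, and 4.8.8 names no periods.
- **Use of the term treatment-emergent.** SAP 4.8.2 defines treatment-emergent adverse events as those on or after first dose, with no end date. An open-ended C-SSRS definition follows the same convention. The fault lies in the treatment-period label.
- **Value of later follow-up.** Protocol 4.4 uses the placebo phase to learn how long the effect lasts, and Protocol 2.2 reports lasting neurological improvement in Phase 2a. If risk persists or emerges on withdrawal, the longer window catches it. That argues for showing later events separately and against dropping them.

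A reader might also infer three stronger points that the documents do not support:

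- **That a suicidality signal is averaged away.** The summary counts patients with at least one event, so every on-drug event stays in.
- **That all the C-SSRS tables run to end of study.** Only the treatment-emergent sentence carries that range; the composite and shift tables do not.
- **That the C-SSRS and adverse event tables cannot be compared.** The entire-study adverse event summary is a near match. What is missing is an explicit C-SSRS split by period.

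**Conclusion.** SAP 4.8.8 and SAP 2.5 contradict each other, and the text must be changed. About 63% of the time covered by the treatment-emergent summary (58% to 70% with the Protocol windows) is off ENT-01, so events arising after drug has stopped would be reported under a treatment-period heading. The window for the composite and shift tables is unresolved.

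The 63% follows from the visit schedule alone. The movement of the risk ratio rests on assumed background rates, an assumed on-drug excess and no carry-over. Under those assumptions the risk difference is nearly unchanged. No safety test is planned, so no power is lost; the issue is how descriptive counts are labelled and read.

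**What to change.** In SAP 4.8.8, assign each C-SSRS assessment to a period by the interval that its since-last-visit recall covers:
- Visits 3 and 4: treatment.
- Visit 5: single-blind placebo.
- Visit 6: washout.
- Early Termination: by date of last dose.

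Applying the SAP 2.5 dates literally would create a new fault. The period ends the day before Visit 4, so the Visit 4 assessment, which covers roughly Days 11 to 26 on drug, would drop out.

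Present the frequency, composite and shift tables for the treatment period, and the frequency and composite tables also for the two later periods. Keep the Visit 3-to-end-of-study table and label it entire study.

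Reconcile the C-SSRS at Early Termination as well. The schedules in Protocol Table 1, Protocol Appendix 2 and SAP Table 1 include it; the procedure list in Protocol 4.7 omits it. The SAP window relies on that assessment.

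The cost is SAP wording and a few extra small descriptive tables. No new data are needed.

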4.8.9 Concomitant Medications

Prior medications are defined as medications taken prior to the first dose of study drug (ENT-01 or placebo). Concomitant medications are defined as medications taken on or after the first dose study drug.

Prior and Concomitant medications will be coded using the WHO Drug dictionary. Results will be tabulated by Anatomic Therapeutic Class (ATC) and preferred term.

The use of prior and concomitant medications will be included in by-subject data listing.

4.8.10 Tolerability

Tolerability will be measured by DLT endpoints. The frequency of occurrence for each tolerability endpoint including recurrent vomiting, recurrent diarrhea, abdominal pain and dizziness will be summarized by treatment group and dose level for the Dose Adjustment period. Percentages will be based on the number of subjects in each dose level in the Safety Population. Since this occurs during the dose adjustment period, the dose level is not fixed for each patient. The number of patients in a dose level will be calculated based on the highest dose level a patient ever took during the Dose Adjustment Period. For example if a patient with low baseline CSBMs had the highest dose of 200 mg, then this patient would be included in the doses of 150, 175, and 200 mg.

5. CHANGES TO PLANNED ANALYSES

As of this date, there have been no changes between the protocol-defined statistical analyses and those presented in this statistical plan.

